### Study protocol:

All women admitted to The Center for Recurrent Pregnancy Loss of Western Denmark from January 2016 to March 2020 were identified in this combined case-control and cohort study and screened for study eligibility. Only patients with a history of  $\geq 3$  consecutive spontaneous pregnancy losses were included. Both biochemical (confirmed by a positive human chorionic gonadotropin (hCG) test) and clinical losses (confirmed by an ultrasound examination and/or histology of aspirated tissue from the uterus) documented in hospital records were accepted. Verified extrauterine pregnancy losses, complete molar pregnancies, and induced abortions of social and genetic reasons were not included in the total number of pregnancy losses. Women with significant uterine malformations, significant parental chromosomal abnormalities, irregular and/or abnormal menstrual cycle length (<22 and >35 days interval), <3 consecutive pregnancy losses (n=26), and/or no p-MBL measurement were excluded. 267 women fulfilled all study criteria. The RPL patients were followed until birth of a liveborn child after RPL or until March 2021, whichever came first.

At the first consultation in The Center for Recurrent Pregnancy Loss of Western Denmark, all women underwent a routine diagnostic work-up including collection of an obstetric and gynecologic history, a routine blood analysis with plasma mannose binding lectin (p-MBL)

measurement, a uterine hydrosonegography, hysteroscopy or hysterosalpingography, and in most cases also a parental chromosomal analysis.

According to the individual health profile, the obstetric history, and the results from blood sample, treatment options such as vaginal progesterone, oral prednisolone, intravenous immunoglobulin (IVIG) infusion, and/or subcutaneous heparin were considered. In patients with an estimated good prognosis, only psychological support and close ultrasound scan monitoring (tender loving care) was offered.

Retrospectively, data was retrieved from the RPL clinical database of The RPL Center in Aalborg University Hospital, Denmark (Data Protection Agency of Region Nordjylland Approval Number 2018-5) in which relevant data is collected on patients from their first consultation and until their contact to the clinic is terminated. Data on perinatal outcomes of all pregnancies before and after RPL was collected at the first consultation, from hospital records, and, when needed, completed by telephone or e-mail correspondence. This included information about mode of conception and delivery, gestational age (GA), birth weight (BW), gender of offspring, volume of peripartum hemorrhage, occurrence of preeclampsia, and perinatal complications. GA was divided into preterm and very preterm birth defined as birth <37 weeks and <32 weeks of gestation, respectively. BW was divided into low and very low BW defined as <2500 g and <1500 g, respectively. Peripartum hemorrhage was divided into moderate hemorrhage of 500-999 ml and severe hemorrhage of  $\geq 1000$  ml lost within 24h after birth including both peripartum hemorrhage during vaginal delivery and caesarean section. Peripartum hemorrhage was routinely estimated and noted by the midwives in the delivery records generally by weighing absorbent bed sheets.

Live births refer to children born alive and who were still alive after 1 week. Miscarriages were divided into early and late miscarriages defined as <12 weeks and 12-21+6 weeks of gestation, respectively. Stillbirth was defined as fetal death  $\geq 22$  weeks of gestation and within 1 week after delivery. pRPL was defined as  $\geq 3$  consecutive pregnancy losses while secondary RPL (sRPL) was defined as  $\geq 3$  consecutive pregnancy losses after the birth of a viable child. Whenever the gender of the fetus was known, it was recorded.

### *Blood samples*

Routine blood analysis comprised the following plasma and genetic biomarkers: plasma level of MBL, autoantibodies (anti-nuclear antibodies [ANA], anti-ds-DNA-antibodies and anti-thyroid peroxidase [TPO] antibodies, lupus anticoagulant [LAC], anti-cardiolipin antibodies [IgG/IgM ACA] and anti- $\beta 2$ -glycoprotein-I antibodies [IgG/IgM aGPL-I]), thyroid stimulating hormone (TSH), homocysteine, the HLA-DRB1 genotype and hereditary thrombophilic factors (the prothrombin- and factor-V Leiden genetic variants, protein S and C, and antithrombin III).

### *MBL assay*

Plasma MBL was measured using enzyme-linked immunosorbent assay (ELISA). Patient plasma was diluted 1:100 in dilution buffer (20 mM Tris + 10 mM CaCl2 + 1 M NaCl + 0,05 % Triton X-100 + 0,1 % BSA, pH 7,4) and incubated on mannose-coated ELISA microtitre wells (Mannose from *Saccharomyces cerevisiae* SIGMA M-7504). After each step, wells were washed 3 times with washing buffer (Tris-buffered saline + 5 mM CaCl2 + 0,05 % Tween 20) and incubated min. 1 hour in room temperature. Biotin conjugated monoclonal anti-MBL (HYB 131-01B-0 1 mg/ml, from Antibody Shop) was added to the wells. Then, after incubation and washing, wells were incubated

in alkaline phosphatase conjugated Streptavidin (Dako code D0396) and finally CSPD substrate was added (ELISA-LIGHT CSPD/Sapphire-II T1023, from Applied Biosystem). After 20 min. the wells were analyzed by a LUMIstar ELISA reader. The analysis used a control patient plasma sample as reference, and a highly purified MBL-standard (SER101) was used for calibration, both tested in several dilutions. This method did not allow precise measurement of the exact plasma concentration of MBL when  $<100 \mu\text{g/l}$  and  $>5000 \mu\text{g/l}$ ; thus, these levels were noted in the data collection as a plasma concentration of  $100 \mu\text{g/l}$  and  $5000 \mu\text{g/l}$ , respectively. The cut-off for low p-MBL used routinely in Danish laboratories is  $<500 \mu\text{g/l}$ .

#### *Ethical approval*

Since only data on routine investigations and interventions in the RPL Center is analyzed and reported, no approval from the ethics committee was needed.

### Statistical analysis plan:

#### *Statistical Analysis*

Data was analyzed using Stata/MP 15.0 for Mac, revision 19 June 2017. Level of statistical significance was defined as  $p < 0.05$ . Patients were divided into 3 subgroups according to their p-MBL levels: low ( $\leq 500 \mu\text{g/l}$ ), intermediate ( $501-3000 \mu\text{g/l}$ ), and high p-MBL group ( $>3000 \mu\text{g/l}$ ).

Cross-sectional data on p-MBL levels were compared between RPL patients and the MBL reference group and analysed using  $\chi^2$  test; first comparing prevalence of  $\leq 500 \mu\text{g/l}$  and  $>500 \mu\text{g/l}$  between the two groups and next the same procedure for intermediate and high levels, respectively. The

relative prevalence of low MBL was compared using prevalence proportion ratio (PPR) with 95% confidence intervals (CI).

A binominal logistic regression analysis was performed to identify the possible prognostic value of low and/or high MBL level on the reproductive outcome in first pregnancy after admission which was adjusted for confounding variables known to influence on the reproductive outcome. The reproductive outcome was defined 1= pregnancy loss and 0= pregnancy>12 weeks or birth in the first pregnancy after admission. Patients with no pregnancy after admission, pregnant at the time of admission, and pregnant after admission but <12 weeks of gestation at final follow-up were not included in the logistic regression analysis of reproductive outcome. p-MBL level was defined as 1=p-MBL level  $\leq 500 \mu\text{g/l}$  and 0= p-MBL level  $>500 \mu\text{g/l}$  in the analysis. Confounders included in the analysis were measured at baseline and involved age (continuous), BMI (continuous), number of pregnancy losses before admission (continuous) and exposure to tobacco smoke (1=yes, 0=no). A linear regression analysis was performed to analyze the effect of p-MBL level on birth weight and GA of first birth before and after RPL; all as continuous variables.

According to perinatal data on first birth before and after admission, the differences in categorical data were determined by  $\chi^2$  test, but in comparisons in which less than 5 numbers were expected the Fisher's exact test was performed. Differences in continuous variables were determined by the two-sample Mann-Whitney U test if data was non-normally distributed, and by t-test if data fitted a normal distribution. When analyzing the previous children's sex, only women with one or more children of same sex born before the RPL diagnosis with a GA >22 weeks were included. Women with sRPL with  $\geq 2$  children of mixed gender were excluded from analyses involving sex of child(ren) born before admission. Sex ratio was reported as a male:female ratio.

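### Does the comparison of MBL levels with the reference group need a named primary test and a ratio for all three levels?

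*Combined protocol and SAP*

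**What the plan says.** The Statistical Analysis section of the SAP sets one threshold for everything: "Level of statistical significance was defined as" p < 0.05. It forms three MBL classes: low (≤500 µg/l), intermediate (501–3000) and high (>3000).

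For the case-control part, "Cross-sectional data on p-MBL levels were compared between RPL patients and the MBL reference group and analysed using" the chi-square test. The first comparison is the prevalence of ≤500 against >500, and "next the same procedure for intermediate and high levels, respectively". The sentence after that gives the only planned estimate for this comparison, a PPR with 95% CI, and limits it to the relative prevalence of low MBL.

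The section then turns to a logistic model within the patients, which is to examine the "possible prognostic value of low and/or high MBL level on the reproductive outcome". The exposure coded for that model is binary, ≤500 against >500.

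No comparison is called primary, and no multiplicity rule is given.

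**The concern.** Three things look unfinished.

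- **No primary comparison.** Several overlapping tests at 0.05 each give more than one route to a significant MBL result. If any of them is read as showing an MBL difference, the false-positive chance exceeds 5%.
- **The comparator for the later tests is not written out.** The plain reading is intermediate against the rest and high against the rest, so three tests in all. One further test of intermediate against high among women above 500 µg/l is also conceivable, so two in all. Under some alternatives the two readings would disagree about high MBL.
- **A ratio for low MBL only.** A p-value for intermediate or high MBL, with no ratio or interval, cannot separate no difference from an imprecise estimate.

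At stake is the status of an isolated significant result for intermediate or high MBL: main finding or side observation.

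**Working it through.** **Inputs.** From the documents: 267 RPL patients (Study protocol), three MBL classes, and 0.05 per test (Statistical Analysis). The documents give neither the size of the reference group nor any class proportions. Both are therefore assumed: reference size m = 100, 200 or 400, and splits written as low/intermediate/high in percent. The plan states no power or familywise figure, so there is nothing of its own to reproduce.

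**Simple bounds.**
- Two tests: sum 2 × 0.05 = 0.10; if independent, 1 − 0.95² = 0.0975.
- Three tests: sum 3 × 0.05 = 0.15; if independent, 1 − 0.95³ = 0.1426.

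The three classes add up to 100%, so three one-versus-rest tests are dependent and 0.1426 overstates the rate.

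**Simulation with no true difference.** Method: 200,000 multinomial draws per setting and Pearson chi-square without continuity correction. Five splits were used (20/60/20, 30/50/20, 25/60/15, 15/60/25, 33/34/33), each at the three reference sizes.

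| Event | Probability |
|---|---|
| Low versus >500 significant | 0.049–0.051 |
| Low, or intermediate versus high, significant | 0.096–0.099 |
| Any of three one-versus-rest tests significant | 0.119–0.125 |
| Intermediate or high significant, low not | 0.069–0.074 |

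The third row is about the first plus the fourth: 0.05 + 0.07 = 0.12. All the excess over 5% comes from studies in which low MBL is not significant and intermediate or high is.

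**How often the two readings disagree on high MBL** (high versus rest against intermediate versus high), for m = 100/200/400, reference split 20/60/20:
- Patients 30/56/14: 0.15/0.21/0.27.
- Patients 20/50/30: 0.10/0.085/0.06.
- Patients 25/58/17: 0.05 to 0.08.
- No difference (the five null splits above): 0.02 to 0.05.

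The range is 2% to 27%, set almost wholly by the assumed alternative.

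**Which reading the text supports.** The procedure just described sets one level against everything else. Repeating it for two levels, with a word that assigns it to each, gives one test per level. A single intermediate-versus-high test would leave that word without a function.

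**Precision of the ratio that is not planned.** For a high-MBL ratio of 1 with assumed prevalence p = 0.20 in both groups, the 95% CI is exp(±1.96·√[(1−p)/(267p) + (1−p)/(mp)]).
- m = 100: √(0.01498 + 0.04000) = 0.2345, CI 0.63–1.58.
- m = 200: √(0.01498 + 0.02000) = 0.1870, CI 0.69–1.44.
- m = 400: √(0.01498 + 0.01000) = 0.1581, CI 0.73–1.36.

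The formula needs only the class counts that the chi-square tests already use.

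**What formal control would cost.**
- *Testing high only after a significant low result.* With 20/50/30 against 20/60/20, power for high falls from 0.50/0.70/0.84 to 0.03/0.03/0.04.
- *Replacing the low-MBL test by one 2×3 chi-square test.* With 30/50/20 against 20/60/20, power falls from 0.49/0.70/0.84 to 0.42/0.63/0.79. The 2×3 test then shows only that some difference exists, not that it lies in low MBL.

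**The case for a change.** The strongest case for acting is that the repair is cheap. One or two sentences could name low versus >500 as primary, state the comparator for the other tests, and add two ratios from the same table. The low-MBL test would lose no power, and no adjustment or gate would be imposed. An order of listing is not a label. Interest in high MBL is explicit elsewhere in the section, so a significant high-MBL result would probably be discussed.

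The facts in that case stand: there is no label, the comparator is left implicit, and a ratio is planned for one level only. What does not follow is that the plan is wrong.

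- The 12% is an error rate for a rule the plan does not contain, namely that any one significant test establishes an MBL difference.
- The stated interest in high MBL belongs to the logistic model of pregnancy outcome within patients, not to the comparison with the reference group.
- The lead comparison can be identified from its position, its ratio, the logistic coding, and the MBL assay section, which names a routine laboratory cut-off for low MBL only.
- The study is retrospective and the plan reports its analysis in the past tense. A primary label attached after results are known gives no prospective error control.

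Reporting ratios for the other two levels would be helpful, but that adds to the report and does not correct the plan.

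**Conclusion.** No change is called for. This is missing detail that an analyst would fill sensibly: three one-versus-rest chi-square tests, low MBL leading, with the class counts available for any further ratio. The low-MBL test keeps its 5% level, as does each of the others taken singly. The rate of about 12% for any of three tests, or 10% for two, matters only if an isolated intermediate or high result is presented as a main finding. The plan makes no such claim.

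The null rates rest on 267 patients and assumed reference sizes and splits, and are stable across them. The 2–27% disagreement between readings is not stable and depends on the assumed alternative. A reader of the results should treat an intermediate or high finding as secondary to low versus >500.

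### The logistic model is meant to assess low and/or high MBL, but its coding has no term for high MBL, so no high-MBL effect on pregnancy loss can be estimated

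*Combined protocol and SAP*

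**What the plan says.** All the relevant text is in the Statistical Analysis section of the SAP.

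- **Groups.** "Patients were divided into 3 subgroups according to their p-MBL levels": low is ≤500, intermediate 501-3000 and high >3000 µg/l.
- **Aim.** The logistic regression is performed "to identify the possible prognostic value of low and/or high MBL level on the reproductive outcome" in the first pregnancy after admission.
- **Outcome.** "The reproductive outcome was defined 1= pregnancy loss and 0= pregnancy>12 weeks or birth in the first pregnancy after admission".
- **Exposure coding.** "p-MBL level was defined as 1=p-MBL level" ≤500 µg/l, with 0 for every value above 500.
- **Other covariates.** Age, BMI, number of earlier losses and tobacco exposure.

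Two other analyses use the upper part of the MBL range. The chi-square comparison of patients with the MBL reference group first splits at 500 and then does "next the same procedure for intermediate and high levels, respectively". A linear regression with continuous p-MBL is used "to analyze the effect of p-MBL level on birth weight and GA of first birth before and after RPL".

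**The concern.** The aim names high MBL, and high has its own definition in the same section, separate from intermediate. The coding then merges the two. A reader is told that high MBL was examined as a prognostic factor, yet the model can give no estimate, confidence interval or test for it. Two errors could follow. The absence of a high-MBL result could be taken for a null result. The single MBL odds ratio could also be read as low against a normal, intermediate level, when its comparator is a mixture of intermediate and high women.

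**Working it through.** **1. What the coding can identify.** The documents give no sample-size or effect figure to reproduce, so the check is on the model itself. At fixed covariates, the log-odds of loss under the two codings are:

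| Group | Planned: b0 + b1·low | Three-level: b0 + b1·low + b2·high |
|---|---|---|
| Low, ≤500 | b0 + b1 | b0 + b1 |
| Intermediate, 501-3000 | b0 | b0 |
| High, >3000 | b0 | b0 + b2 |

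Under the planned coding, high minus intermediate is b0 − b0 = 0 by construction. The design has rank 2 for three groups. Under the three-level coding the rank is 3 and the contrast is b2, which is estimable. This step needs no assumption about the data.

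**2. Whether another analysis fills the gap.** The chi-square steps compare MBL prevalence between patients and the reference group, not pregnancy outcome. The linear regression concerns birth weight and gestational age. The tests at the end of the section concern perinatal data and the sex of earlier children. No second logistic model is described.

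**3. Low versus >500 against low versus intermediate.** All inputs here are assumed, and the calculation is unadjusted. Let f be the group shares, with loss of 35% in both low and intermediate women, so that the low-versus-intermediate odds ratio (OR) is 1.00.

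Pooled risk above 500 = (f_int × 0.35 + f_high × p_high) / (f_int + f_high)

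Planned OR = odds(0.35) / odds(pooled risk)

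For a 20/55/25 split with p_high = 0.25, the pooled risk is (0.55 × 0.35 + 0.25 × 0.25) / 0.80 = 0.3187, and the OR is 0.5385 / 0.4679 = 1.15. The full set for this split is:

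| Loss in high group | Pooled risk | Planned OR |
|---|---|---|
| 25% | 0.3187 | 1.15 |
| 30% | 0.3344 | 1.07 |
| 35% | 0.3500 | 1.00 |
| 40% | 0.3656 | 0.93 |
| 50% | 0.3969 | 0.82 |

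The two extremes are 1.08 and 0.89 for a 15/70/15 split, and 1.24 and 0.74 for 25/40/35.

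**4. What a three-level factor costs in precision.** The split is assumed.

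- The standard error (SE) for low is multiplied by sqrt[(1/0.20 + 1/0.55) / (1/0.20 + 1/0.80)] = 1.044. The multiplier is 1.016 for 15/70/15 and 1.104 for 25/40/35.
- For high versus intermediate at 35% loss, unadjusted, SE(log OR) = sqrt[(1/f_high + 1/f_int) / (N × 0.35 × 0.65)]. The 95% CI is the OR divided and multiplied by exp(1.96 × SE).

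| Split | N = 267 | N = 150 (assumed) |
|---|---|---|
| 20/55/25 | SE 0.309, factor 1.83 | SE 0.413, factor 2.25 |
| 15/70/15 | factor 2.05 | factor 2.60 |

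The Study protocol section states that "267 women fulfilled all study criteria". That is a ceiling. The SAP leaves out of the model women with no pregnancy after admission, those already pregnant at admission and those under 12 weeks at final follow-up.

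**5. Multiplicity.** With a 20/55/25 split, the two contrasts against a shared reference have correlation (1/0.55) / sqrt[(1/0.20 + 1/0.55)(1/0.25 + 1/0.55)] = 0.289. Reading each at two-sided 0.05 gives a family-wise error of about 0.095 (bivariate normal).

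**The case against.** The strongest reply is that this is an objective worded more widely than the model, not a faulty estimate. The coding is stated openly, the SAP names >500 as the comparator, and the resulting odds ratio is unbiased for that contrast. A split at 500 follows the routine laboratory cut-off given in the MBL assay section and the first cross-sectional comparison. Because the aim is worded with and/or, a low-only model could be said to meet one branch of it. The illustration in step 3 of the working measures a misreading that the SAP does not itself make, on assumed inputs.

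Most of that is fair. The dichotomy is legitimate, and step 3 is secondary. It does not supply the missing estimate, however. If only the low branch is intended, the plan should say so. Reading high loosely as anything above 500 conflicts with the SAP's own definition of >3000, and it would still leave a single contrast.

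Two further points stand as cautions. The text is in the past tense and follow-up ended by March 2021, so a model changed now may be post hoc; the documents do not show when the plan was written. Precision for a high-MBL term would also be limited, more so if the high group is small.

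**Conclusion.** The concern holds: the plan is wrong as written. Under the stated coding the high-MBL odds ratio for pregnancy loss is not estimable whatever the data, so part of the stated prognostic question goes unanswered. This conclusion rests on the text alone.

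The results support a statement about ≤500 versus >500 µg/l only. The distance between that odds ratio and a low-versus-intermediate one cannot be known from the documents. It is zero if high and intermediate risks are equal, and under the assumed inputs it is modest unless the high group is large and its risk clearly different. The data do not stand in the way: the assay reports values up to 5000 µg/l, so women above 3000 can be identified.

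**What to change.** Preferred change: enter p-MBL in the logistic model as the SAP's three-level factor with 501-3000 as reference. Report adjusted odds ratios with 95% CIs for low and for high. Also report low versus >500, which matches the cross-sectional comparison. Name one primary contrast, or test the two p-MBL terms jointly (2 df) at 0.05 before reading each. If outcome results were already known when the change is made, label the three-level analysis post hoc.

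The cost is SAP wording and one extra parameter, with no new data. The standard error for low rises by about 4% (2% to 10% over the splits considered). The high-MBL interval will be wide, so a non-significant result should not be read as no effect.

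Minimum alternative: leave the model as it is, remove high MBL from the stated aim, and confine all conclusions to ≤500 versus >500 µg/l. This costs only wording, but leaves the high-MBL question unanswered.

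### Inclusion near the March 2021 cut-off depends on outcome: pregnancies begun in the last 12 weeks count only if lost, and late-begun pregnancies over-represent preterm births. The effect is small and a start-date rule removes it

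*Combined protocol and SAP*

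**What the plan says.** The Study protocol section sets the calendar. The cohort is "All women admitted to The Center for Recurrent Pregnancy Loss of Western Denmark from January 2016 to March 2020", and "The RPL patients were followed until birth of a liveborn child after RPL or until March 2021, whichever came first". It adds that "267 women fulfilled all study criteria". The last women admitted thus have about a year of follow-up.

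The Statistical Analysis section defines the logistic outcome: "The reproductive outcome was defined 1= pregnancy loss and 0= pregnancy>12 weeks or birth in the first pregnancy after admission". Among the exclusions are women "pregnant after admission but <12 weeks of gestation at final follow-up were not included in the logistic regression analysis of reproductive outcome". A loss has no matching requirement on when the pregnancy began.

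The same section regresses "birth weight and GA of first birth before and after RPL" on p-MBL and compares perinatal data on the first birth before and after admission. Neither analysis limits when the pregnancy began. The Study protocol section defines preterm birth as delivery before 37 weeks and splits losses by timing: "Miscarriages were divided into early and late miscarriages defined as <12 weeks and 12-21+6 weeks of gestation, respectively".

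**The concern.** Pregnancies near a fixed closing date have unresolved outcomes. The plan removes those still ongoing below 12 weeks but keeps losses from the same calendar weeks. Whether such a pregnancy is counted then depends on the outcome being modelled, and every counted pregnancy from that window is a loss.

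The closing date also acts on post-RPL births. A pregnancy that began less than 37 weeks before it can contribute only a preterm birth. One that began 37 to 42 weeks before can contribute a preterm birth or an earlier term birth, but not a later one. Births before admission had already happened and are not cut off, so any before/after contrast is affected on one side only.

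At stake are the reported loss proportion, the preterm share and the gestational-age distribution after RPL.

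**Working it through.** The documents give no loss proportion, preterm proportion, time to pregnancy or number excluded at the cut-off, so there is no planned figure to reproduce. The mechanism follows from the text alone; its size needs assumptions.

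**Inputs from the documents.** Admissions January 2016 to March 2020; cut-off March 2021; at most 267 women; the outcome codes and exclusion above; preterm below 37 weeks.

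**Assumptions (not in the documents).** Uniform admission over 221 weeks; cut-off 48 or 52 weeks after the last admission; exponential time to first pregnancy with median 3 to 24 months; early loss 30% or 45%, at a mean of 7.5 weeks; late loss in 3% of pregnancies passing 12 weeks; 10% of births preterm.

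**Step 1: formula.** Let *d* be the share of first pregnancies dropped as ongoing below 12 weeks, *p* the true loss proportion and *r* the loss risk still facing those dropped. The observed proportion is (p − rd)/(1 − d), so the shift is d(p − r)/(1 − d). It is upward whenever r < p, as expected for pregnancies that have already survived some weeks.

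**Step 2: counts.** Take 200 included pregnancies with 70 losses (35%), *k* dropped and r = 20%. The proportion with the dropped pregnancies restored is (70 + 0.2k)/(200 + k):

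- k = 2: 70.4/202 = 34.85%, a shift of 0.15 points
- k = 5: 71/205 = 34.63%, a shift of 0.37 points
- k = 10: 72/210 = 34.29%, a shift of 0.71 points

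The last case drops 10/210 = 4.8%, more than any simulated setting.

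**Step 3: simulation of the written rules** (4 million women per setting; selected rows).

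| Cut-off after last admission (weeks) | Median months to pregnancy | Early loss | Dropped (%) | Loss (%), true → as written | Preterm (%), true → as written |
|---|---|---|---|---|---|
| 52 | 3 | 30% | 0.27 | 32.10 → 32.14 | 10.00 → 10.09 |
| 52 | 6 | 30% | 0.90 | 32.14 → 32.26 | 10.00 → 10.15 |
| 52 | 12 | 30% | 1.78 | 32.11 → 32.35 | 9.99 → 10.17 |
| 48 | 24 | 30% | 2.70 | 32.10 → 32.44 | 10.02 → 10.31 |
| 48 | 24 | 45% | 2.41 | 46.65 → 47.11 | 10.00 → 10.32 |

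These figures are net of a small opposite effect: ongoing pregnancies past 12 weeks are coded 0 although some may still be lost. A second set-up (mean 4 to 24 months, 35% losses) gave shifts of about 0.03 to 0.3 points. Across all set-ups, including one that allows the first birth to follow a further loss, the preterm share rises by about 0.1 to 0.4 points and mean gestational age after RPL falls by about 0.05 to 0.16 days.

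**Step 4: compare with sampling error.** For 35% in an assumed 200 pregnancies, SE = √(0.35 × 0.65/200) = 3.4 points. For 10% preterm in an assumed 130 births, SE = √(0.10 × 0.90/130) = 2.6 points.

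**Step 5: MBL odds ratio.** With equal timing in both MBL groups it does not move (1.761 true, 1.761 as planned). If low-MBL women take twice as long to conceive, a null odds ratio goes from 0.999 to 1.005 (medians 6 and 12 months) or from 1.003 to 1.014 (24 and 48 months). With 200 pregnancies, 25% low MBL and 35% losses, the SE of the log odds ratio is √[1/(50 × 0.35 × 0.65) + 1/(150 × 0.35 × 0.65)] = 0.34. The larger shift, ln(1.014/1.003) = 0.011, is about 3% of that.

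**Step 6: after the change.** Keeping only pregnancies begun at least 12 weeks before the cut-off returns early loss to 30.0% and 45.0%, against 30.05–30.43% and 45.05–45.52% as written.

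**The case against.** The strongest reply is that the quoted rule governs a logistic regression on MBL, and selection on outcome alone leaves an odds ratio unchanged. The SAP names no loss proportion as a target. Excluding an ongoing pregnancy below 12 weeks is also sensible in itself, because its outcome is not yet determined under the coding. Admission closed about a year before follow-up ended, which already limits the problem: losses from the critical window come to about 0.1 to 1 per 200 included pregnancies. All of this stands. What remains is that the rule is one-sided and that nothing else in the plan corrects it.

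Two stronger readings are tempting. A reader might infer that the MBL odds ratio, or the MBL regressions on gestational age and birth weight, are distorted. That requires time to conception to differ by MBL level, which the documents nowhere suggest. Even with means of 4 against 24 months, a null odds ratio reaches only about 1.013, and the between-group difference in gestational age is under 0.1 day, against an SE of about 2.8 days for an assumed 130 births. Birth weight was not simulated separately.

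A reader might also infer that late-begun pregnancies yield only preterm births. That holds only for starts less than 37 weeks before the cut-off. Across the whole 42-week window, about 26 to 32% of observed births were preterm in the simulations, so most were term.

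The preterm point does not follow from the logistic exclusion. It rests on the fixed end of follow-up together with the perinatal analyses.

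**Conclusion.** The outcome-dependent inclusion is certain from the text and its direction is upward for both loss and prematurity. Its size depends on conception times and loss rates that the documents do not give. Over the ranges assumed it is at most about half a point on the loss proportion and 0.4 points on the preterm share. It is no threat to the MBL conclusions and is a minor, inexpensive improvement. The number of women excluded as ongoing below 12 weeks is not stated, so a reader cannot confirm from the plan that the effect is negligible in this cohort.

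A related ambiguity affects the remedy: a loss at 12 to 21+6 weeks satisfies both outcome codes as written, being a pregnancy loss and also a pregnancy that passed 12 weeks.

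**What to change.** Define eligibility by the date the pregnancy began, not by its outcome.

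- **Logistic model:** include first pregnancies that began at least 12 weeks before final follow-up, whatever their outcome, and exclude all later ones, losses included. Define the event as loss before 12 weeks, so that later losses no longer fit both codes.
- **Post-RPL gestational age, birth weight and preterm analyses:** include only births from pregnancies that began at least 42 weeks before final follow-up.
- **Reporting:** state how many pregnancies and births each rule excludes.

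A time-to-event analysis by gestational age, censored at the cut-off, would be an alternative for the loss outcome.

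The cost is SAP wording and a date filter on existing records. About 1 to 3% of pregnancies or births are lost, with slightly lower precision. For the logistic model the additional loss is smaller still, because the ongoing pregnancies are already excluded. The event also becomes early loss rather than any loss, so losses at 12 to 21+6 weeks should be described separately. For biochemical losses the start date may have to be approximated.
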